4.1.3 Product Dispensation

A new prescription will be required after each screening — on days 0, 14, and 28 — in order for the site pharmacist to dispense each assigned study product to participants.

4.2 Study Product Preparation for Topical Administration

The site pharmacist will pre-fill seven 5 mL amber-colored topical syringes with 2 mL of study product, and assemble them as a one-week supply for each participant. The syringes must be stored at room temperature, and will be given a 30-day expiration date.

4.3 Study Product Formulations

4.3.1 BufferGel

The active ingredient of BufferGel is the hydrogen ion. BufferGel is formulated to buffer the concentration of free hydrogen ions at the level normally found in the vaginal lumen, 0.1 mM (pH 3.8 - 4.0). Hydrogen ions are buffered (released or bound) by abundant carboxyl groups on the carbopol 974P polymer which constitutes the major nonaqueous component (4 percent polymer, 94 percent water) of BufferGel. The additional constituents of BufferGel are all USP23/NF18: dibasic potassium phosphate, magnesium sulfate, dibasic sodium phosphate, sorbic acid, monobasic sodium phosphate, and disodium EDTA. BufferGel is supplied in 100 gram tubes, and must be stored at room temperature.

4.3.2 PRO 2000/5 Gel (P)

PRO 2000/5, the active ingredient of PRO 2000/5 Gel (P), is a polyanionic polymer consisting of alternating 2-naphthalene sulfonic acid sodium salt and methylene units. The weight-average molecular weight ($M_{\rm W}$) is 5 ± 1 kilodaltons and the polydispersity ($M_{\rm W}/M_{\rm B}$), a measure of molecular weight distribution, is 1.2. PRO 2000/5 is synthesized by the acid catalyzed condensation of 2-naphthalene sulfonic acid with formaldehyde, followed by neutralization and molecular weight fractionation. PRO 2000/5 Gel (P), 4%, is an aqueous gel formulation containing four percent (w/w) PRO 2000/5, Carbopol 1382, lactic acid, trolamine, methylparaben, propylparaben, and sodium benzoate. It is buffered to pH 4.5. PRO 2000/5 Gel (P) is supplied in 3.7 gram tubes, and must be stored below 35° C.

4.3.3 Placebo Gel

The placebo gel is K-Y Jelly, a licensed, commercially available water-based lubricant that contains chlorhexidine gluconate and methylparaben as preservatives as well as glucono delta lactone, glycerine, hydroxyethylcellulose, purified water, and sodium hydroxide. It should be stored at room temperature.

4.4 Study Product Supply, Acquisition, and Accountability

4.4.1 Product Supply

BufferGel will be provided by ReProtect, LLC. PRO 2000/5 Gel (P) will be provided by Interneuron Pharmaceuticals, Inc. The placebo gel must be purchased by the study site pharmacy from a commercial vendor.

4.4.2 Product Acquisition

BufferGel, PRO 2000/5 Gel (P), and syringes for topical administration will be made available to the study site through the NIAID Clinical Research Products Management Center. The site pharmacist will obtain these products from the Clinical Research Products Management Center according to the instructions in the manual "Pharmacy Guidelines and Instructions for AIDS Clinical Trials Group," in the section entitled "Investigational Agent Control." The study site will purchase the placebo gel from a commercial vendor.

4.4.3 Product Accountability

The site pharmacist must maintain complete records of all study products agents received from the NIAID Clinical Research Products Management Center and subsequently dispensed to study participants. Supplies of the placebo gel also must be accounted for in a similar manner. All unused BufferGel, PRO2000 Gel (P), and syringes must be returned to the NIAID Clinical Research Products Management Center after the study is completed or terminated.

4.5 Adherence Assessment

Participants will record in their study diaries the date and time of each product application, as well as the date and time at which each application is washed off. The diaries also will collect information on participant compliance with other protocol requirements (e.g., abstinence from sexual intercourse). Participants will return all used and unused product syringes to the study site at their Day 7, 21, and 35 visits. At these visits, Study staff will assess adherence with the study product use regimen by reviewing the study diaries, counting the number of used and unused syringes, and discussing participants' experiences.

Application of all three study products on all seven consecutive assigned nights will be targeted, however lapses of product use on one or two assigned nights will be accommodated, as follows:

Participants who miss one application will be instructed to complete the remaining application on the night following the seventh assigned night, and then to present for their post-use evaluation visit. In such cases, participants will have completed at least one consecutive nightly application immediately prior to the evaluation.

Participants who miss two applications will be instructed to complete two applications on the two consecutive nights following the seventh assigned night, and then to present for their post-use evaluation visit. In such cases, participants will have completed at least two consecutive nightly applications immediately prior to the evaluation.

Note: In some cases, this scenario may result in participants completing a total of eight product applications; additional product supplies will be provided to participants as needed.

Participants who complete seven applications of each product on seven consecutive nights, or adhere to the two scenarios just described, will be considered "adherent" to the product use regimen. In addition to the above, participants who experience an adverse event (AE) that requires product discontinuation (see Appendix III), but apply study products on all nights prior to experiencing the AE also will be considered "adherent" to the product use regimen.

Although all available outcome data from all enrolled study participants will be included in study data analyses, all "non-adherent" participants will be withdrawn from the study, and one additional participant will be enrolled in the study for each participant who either drops out of the study or is withdrawn due to "non-adherence." As such, all analyses will include at least 24 "adherent" participants.

Note: Participants will not routinely be withdrawn from the study due to intermittent non-compliance with other protocol requirements (e.g., abstinence from sexual intercourse), provided they are willing to try to become compliant for the remainder of the study.

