3.4 Participant Withdrawal

Once a participant has enrolled in the study, the study site will make every reasonable effort to retain him for the entire five-week study period. Given the small study sample size, and the importance of ascertaining all safety outcomes among study participants, 100 percent retention of enrolled participants is targeted. Study site staff are responsible for developing and implementing local standard operating procedures to achieve complete follow-up.

However, participants may withdraw from the study for any reason at any time. The Investigator also may withdraw participants from the study in order to protect their safety (e.g., due to intolerance of the study products or development or exacerbation of a concomitant medical condition) and/or if they are unwilling or unable to comply with required study procedures. In particular, participants who experience vesiculation, bullous reaction, or ulceration, or are diagnosed with a confirmed STD, will be followed until the condition resolves and then will be withdrawn from the study (see Appendix III). Participants who voluntarily withdraw from the study, are withdrawn by the Investigator, or are not adherent to the study product application regimen, as defined in Section 4.5, will be replaced.

Participants also may be withdrawn if the study sponsor or regulatory authorities terminate the study prior to its planned end date.

Every reasonable effort will be made to complete a final evaluation of participants who terminate from the study prior to Day 35, and study staff will record the reason(s) for all withdrawals from the study in participants' study records.

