7.2 Sample Size and Accrual

A minimum of 24 "adherent" (as defined in Section 4.5) HIV-infected men — 12 circumcised and 12 uncircumcised — will be included in the study. Based on preliminary estimates, it is expected that 9-12 participants will be enrolled per month, and that 24 participants will be accrued within three months. Additional participants may be included in the study as needed to replace non-adherent participants, as described in Section 4.5.

The table below presents the probability of observing either zero or two or more safety outcomes among groups of 12 (circumcised or uncircumcised) or 24 (circumcised and uncircumcised) participants for various "true" event rates.

	P(0 events observed)		P(2+ events observed)	
Event Rate	n=12	n=24	N=12	n=24
1%	.89	.79	<.01	.02
5%	.54	.29	.12	.34
10%	.28	.08	.34	.71
20%	.07	.005	.73	.97
30%	.01	<.001	.91	>.99
40%	.002	<.001	.98	>.99
50%	<.001	<.001	>.99	>.99

Based on the above, if any safety outcome occurs at a rate of less than five percent, then the probability of observing at least two such events is 12 percent among 12 participants (e.g., the subset of uncircumcised men) and 34 percent among 24 participants. Alternatively, 12 participants provide 91 percent power to exclude event rates of 30 percent or more, and 24 participants provide 97 percent power to exclude event rates of 20 percent or more.

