Appendix III

HPTN 032 Male Tolerance Study of BufferGel and PRO 2000/5 Gel (P)

ASSESSMENT, FOLLOW-UP, AND TREATMENT OF SIGNS AND SYMPTOMS

Condition	Product Use	Further Evaluation	Follow-up
Irritative symptoms	If no signs are observed	None	Re-examine within 3 days if
(itching, burning, pain, etc.)	on exam or urine test,		symptoms persist.
	continue current product		
	use; otherwise follow		
	guidelines for observed		
	signs.		
Questionable Erythema	Continue current product	None.	Re-examine at end of product use
	use.		period (at next scheduled Post-Use Evaluation Visit). Consider for
			crossover to next product.
Definite Erythema	Discontinue current	None.	Re-examine within 3 days.
Bernite Liyuenia	product use.	rvone.	Consider for crossover to next
	product use.		product.
Erythema and Induration	Discontinue current	None.	Re-examine within 3 days.
	product use.	1,01101	Consider for crossover to next
			product.
Vesiculation	Discontinue product use.	None.	Re-examine within 3 days.
			Follow-up to resolution then
			discontinue from study.
Bullous Reaction	Discontinue product use.	None.	Re-examine within 3 days.
			Follow-up to resolution then
			discontinue from study.
Ulceration	Discontinue product use.	Culture and DFA for	Re-examine within 3 days. Treat
		herpes simplex virus 2; evaluate for other causes	infection (if diagnosed) with
		(e.g., syphilis, chancroid)	appropriate antibiotic therapy. Follow-up to resolution then
		if suspected based on	discontinue from study.
		clinical judgement.	discontinue from study.
Other Epithelial Change	Continue or discontinue	None.	Re-examine within 3 days.
guner Zpranemar emange	current product use	T toller	Consider for crossover to next
	based on clinical		product.
	judgement.		•
Positive urine LE	Discontinue current	Urine culture and urine	Re-evaluate in 5-7 days, when
(>trace)	product use.	LCR for gonorrhea and	urine test results are available.
		chlamydia.	Treat infection (if diagnosed) with
			appropriate antibiotic therapy. If
			STD is diagnosed, follow to
			resolution, then discontinue from study. Otherwise consider for
			crossover to next product.
Confirmed STD	Discontinue product use.	None.	Treat with appropriate antibiotic
	2 iscontinue product disc.	Tione.	therapy. Follow to resolution, then
			discontinue from study.

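### Section 4.5 withdraws and replaces men who stop a gel for symptoms without signs, while Section 4.6 says men who discontinue for an AE are not routinely withdrawn

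*Protocol*

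**What the plan says.** All references are to the protocol.

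- **Missed nights (4.5).** "lapses of product use on one or two assigned nights will be accommodated", provided that they are made up directly after the seventh assigned night. Anything beyond that is non-adherence unless the AE exception applies.
- **AE exception (4.5).** The exception reads: "participants who experience an adverse event (AE) that requires product discontinuation (see Appendix III), but apply study products on all nights prior to" that event also count as adherent.
- **Consequence (4.5, 3.4).** All non-adherent men are withdrawn. On replacement the text says: "one additional participant will be enrolled in the study for each participant who either drops out of the study or is withdrawn due to" (the cause it names is non-adherence). Section 3.4 repeats the replacement rule.
- **Appendix III.** In the row headed "Irritative symptoms", the product-use rule begins "If no signs are observed" on examination or urine test. In that case current product use continues. Otherwise the row for the observed sign applies.
- **Section 4.6.** A man who discontinues one product because of an AE, other than four listed conditions, is not withdrawn as a matter of routine. The Investigator and the Protocol Clarifications Team judge whether he continues product use or crosses over after a washout.
- **Section 3.4.** "100 percent retention of enrolled participants is targeted", because the sample is small and all safety outcomes need to be ascertained.
- **Endpoints and analysis (7.1.1, 7.6).** Reported urethral pain or burning and penile itching count as a primary endpoint without any sign. Every enrolled man is tabulated. Products are not compared statistically, but the plan looks at whether individual men had similar findings across products.
- **Sample size (7.2).** A minimum of 24 adherent "HIV-infected men — 12 circumcised and 12 uncircumcised — will be included in the study".

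**The concern.** In a tolerance study, giving up a gel because it burns or itches is a tolerability result. Section 4.5, read with Appendix III, handles it as a compliance failure when no sign is found, because discontinuation was not required. The man is then withdrawn and someone else takes his place. Section 4.6 points the other way for the same man, so site staff could follow either section and handle two identical cases differently.

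What is at stake is the data on the remaining gels from men who reacted to an earlier one. Section 7.6 relies on those data to see whether the same men react to more than one product. The text also sits oddly beside the note in 4.5 that men who intermittently breach other requirements, such as sexual abstinence, are not routinely withdrawn.

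**Working it through.** **1. The plan's own figures.** Section 7.2 tabulates the probability of 0 and of 2 or more events. With P(2+) = 1 − (1−p)^n − n·p·(1−p)^(n−1):

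- n = 12, p = 0.30: 0.915 (stated .91)
- n = 24, p = 0.20: 0.967 (stated .97)
- p = 0.05: 0.118 for n = 12 and 0.339 for n = 24 (stated .12 and .34)

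The table reproduces, and this point does not dispute it.

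**2. One man traced through the text.** He reports burning, has no sign on examination and a negative urine test, and stops applying the gel for three or more nights.

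| Step | Source | Result |
|---|---|---|
| Has he met a primary endpoint? | 7.1.1 | Yes, by report alone |
| Is discontinuation required? | Appendix III | No, product use continues |
| Does the AE exception apply? | 4.5 | No, it needs an AE that requires discontinuation |
| Is he within the missed-night allowance? | 4.5 | No, it covers one or two nights, made up |
| Outcome under 4.5 and 3.4 | 4.5, 3.4 | Non-adherent, withdrawn, replaced |
| Outcome under 4.6 | 4.6 | Not routinely withdrawn; crossover considered |

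A man who misses one or two nights and does not make them up follows the same path.

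**3. How many men.** Section 1.1 gives symptom rates in HIV-uninfected men of about 1/3 (PRO 2000/5 Gel), 1/8 (BufferGel) and 1/6 (K-Y Jelly, the placebo here). The fraction f of symptomatic men who stop is not in the documents; 10%, 25% and 50% are assumed. For a product with symptom rate r, expected stoppers among 24 men = 24·r·f, and P(at least one) = 1 − (1 − r·f)^24.

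| Product | f = 10% | f = 25% | f = 50% |
|---|---|---|---|
| PRO 2000/5 Gel (1/3) | 0.8 men, 56% | 2.0 men, 88% | 4.0 men, 99% |
| K-Y Jelly (1/6) | 0.4 men, 33% | 1.0 man, 64% | 2.0 men, 88% |
| BufferGel (1/8) | 0.3 men, 26% | 0.75 men, 53% | 1.5 men, 79% |

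**4. Later-product data lost.** With four men per sequence (7.3), each product comes first for 8 men. Expected period-1 stoppers are 8 × (1/8 + 1/3 + 1/6) × f = 5f, that is 0.5, 1.25 or 2.5 men, each losing two products. Period-2 stoppers number at most 5f and lose one product each. The loss is thus at most 2 × 5f + 5f = 15f product-weeks, that is 1.5, 3.75 or 7.5 of the 72 (24 × 3) planned for the first 24 men. Period-3 stoppers lose no other product. Replacements refill the cells, but with different men.

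**5. Effect on the planned rates.** In a simulation of 4,000 trials per scenario, each stopper was withdrawn and replaced within his sequence, and all enrolled men were tabulated. Symptoms were either independent across products or confined to a susceptible 60% or 40% of men (assumed). The true PRO 2000/5 Gel rate was 33.3%.

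| Symptom structure | f = 10% | f = 25% | f = 50% |
|---|---|---|---|
| Independent | 33.5% | 33.3% | 33.4% |
| 60% susceptible | 32.7% | 32.6% | 31.7% |
| 40% susceptible | 32.8% | 31.7% | 29.7% |

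The largest fall is 33.3 − 29.7 = 3.6 points. In that same scenario BufferGel falls from 12.5% to 10.2% (2.3 points) and K-Y Jelly from 16.7% to 13.6% (3.1 points). Under independence there is no bias, since the replacement has the same expected risk on later products. Enrolment rises to between 25.5 and 33.5 men on average. As a check, for independence and f = 50%, 24 / [(1 − 1/16)(1 − 1/6)(1 − 1/12)] = 24 / 0.716 = 33.5.

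**The case against.** The strongest reply is that the outcome is not settled. Section 4.6 is not limited to AEs that require discontinuation and can be read to keep these men in the study. That stands, and it is why the point is a contradiction to resolve and not a certain loss of data. It does not remove the problem, because 4.5 withdraws all non-adherent men and makes no exception for those covered by 4.6.

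The affected path is narrow. The man must have no finding that requires stopping, must stop against the continue-use guidance, and must exceed the missed-night allowance. The earlier trials described their symptoms as mild. Some symptomatic men will also have signs that bring them inside the exception, so the counts above lean high. All of this stands.

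The conflict with 3.4 is weak. Full retention is a target, and the same section provides for withdrawal and replacement and asks for a final evaluation of men who leave early. Section 6 follows AEs to resolution or stabilisation in any case.

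A reader might infer that the rule selects tolerant men, so that reported rates describe only those who coped with the gels. The documents do not support this. Sections 4.5 and 7.6 include all enrolled men, so the reaction that made a man stop stays in both numerator and denominator for that product. The 24 adherent men are a minimum to be included. No analysis restricted to them is planned, and a rate computed in them alone says nothing about the planned tabulations.

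**Conclusion.** The point holds as an inconsistency with a modest consequence. Section 4.5 with Appendix III makes a man who stops for symptoms without signs non-adherent, to be withdrawn and replaced; 4.6 would ordinarily keep him. If 4.5 is followed, men who stop in period 1 or 2 contribute nothing on their remaining products, which weakens the within-man look in 7.6 for the men most informative for it.

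The effect on the tabulated rates is about 0 to 4 points, or under one man in 24 (0.036 × 24 = 0.9), and arises only through later-period data. These sizes rest on symptom rates from HIV-uninfected men and on assumed stopping fractions and susceptibility. The textual conflict rests on no assumption.

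**What to change.** Reconcile Sections 3.4, 4.5, 4.6 and Appendix III on men who stop for symptoms without signs:

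- Record applications that the participant attributes to a symptom as missed for an AE-related reason, not as non-adherence.
- State that such missed applications do not trigger automatic withdrawal under 4.5.
- Tabulate them by product as a tolerability outcome.
- Keep these men in scheduled follow-up. Leave further product use to the existing 4.6 process; no change to a product-use rule is proposed here.

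Men who miss applications for unrelated reasons need no new provision.

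The cost is protocol wording, a reason field for missed applications and a few extra visits. Some men will have short exposure on the stopped product, which loosens the minimum exposure that 4.5 is meant to secure. They should be reported as such, with the number of applications completed.

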4.6 Toxicity Management

Participants will be instructed to report all AEs to study staff at the time of AE onset. Participants who report AEs deemed by the study clinician — based on the participant's description — to be associated with use of study products will be instructed to wash off the product with plain warm water and to present to the study site for an in-person evaluation (except in potential emergency situations, in which participants will be instructed to present to an emergency room). Based on the results of this evaluation, the Investigator will recommend either continuation or discontinuation of product use, consistent with the criteria in Appendix III. The investigator also may prescribe or recommend the use of medications or other preparations to treat the AE.

Participants who discontinue use of one study product due to an AE — other than vesiculation, bullous reaction, ulceration, or confirmed STD — will not routinely be withdrawn from the study. In consultation with the Protocol Clarifications Team (see Section 10.1) the Investigator will judge whether the participant should continue product use and/or be "crossed over" and, following a washout period, begin use of the other study product(s). Participants who experience vesiculation, bullous reaction, or ulceration, or are diagnosed with a confirmed STD, will be followed until the condition resolves and then will be withdrawn from the study. All AEs will be followed and reported as described in Section 6.

4.7 Concomitant Medications

Enrolled participants may continue use of all concomitant medications — except exclusionary topical preparations applied to the penis — during this study. All concomitant medications will be recorded on applicable study case report forms. Medications used for the treatment of AEs that occur during study participation also will be recorded on applicable case report forms.

5 STUDY PROCEDURES

5.1 Pre-Screening

If desired, study staff may pre-screen potential study participants for the study by telephone or in-person at off-site locations. During these interactions, study staff may explain the study (including the requirements to abstain from masturbation and sexual intercourse during product use periods) to participants and ascertain presumptive eligibility, to be confirmed at a Screening and Enrollment Visit at the study site. Sensitive pre-screening data may be recorded and stored at the study site in the absence of written informed consent, provided that the information is collected in such a manner that it cannot be linked to participant identifiers.

5.2 Screening and Enrollment Visit (Day 0)

Note: If required, the procedures specified below may be completed over the course of two or more visits. Study documentation should specify the dates upon which each procedure is performed, and the final visit should be treated as "Day 0." The timeframes for eligibility determination specified in Section 3 are relative to Day 0.

- Confirm participant identity and assign Participant ID number.
- Explain the purpose of the visit and the informed consent and eligibility determination processes.
- Obtain written informed consent.

- Collect participant contact and locator information.
- Administer Demographics Form.
- Obtain medical history.
- Obtain written permission to obtain medical records documenting HIV status and most recent CD4 count.
- Assess vital signs and perform symptom-directed physical exam.
- Perform genital exam, including visual inspection of the penile shaft, foreskin, and glans; use hand held lens to examine any observed abnormalities. Take digital photograph of any observed abnormalities, and of normal area(s) if needed for clinical decision-making and/or documentation purposes.
- Collect urine and perform dipstick urine LE test.
- Determine eligibility based on medical history, exam findings, and urine test results.
 - \Rightarrow If the participant does not meet the study eligibility criteria, he is ineligible; discontinue participation.
 - ⇒ If the participant does meet the study eligibility criteria, proceed with the following:
 - Obtain the next sequential randomization envelope and determine the participant's random assignment.
 - Provide the participant with the first assigned study product, a study diary, and verbal and written instructions for their use.
 - Instruct the participant to abstain from sexual intercourse, masturbation, and other activities that may cause penile irritation or injury.
 - Provide contact information and instruct the participant to contact the study site to ask questions and/or report any symptoms they may have during the study period.
 - Schedule Day 7 Post-Use Evaluation Visit.
 - Complete and submit all required data collection forms.

